6.3.2 Key Secondary Outcome Analysis

The key secondary outcome variable is the proportion of subjects experienced response at week 16. 95% exact Clopper-Pearson confidence interval (CI) of the proportion of responders will be provided within each parent study treatment group and overall, as well as subgroup by anti-TNF agent use. Parent study treatment comparison will be performed using Fisher's exact test.

The same logistic regression analysis as the primary output variable will also be performed.

6.3.3 Selected Other Secondary Endpoints/Variables

6.3.3.1 Time to Event Endpoints/Variables Analysis

The Time to event endpoints that will be analyzed includes:

- Time to remission
- Duration of remission
- Time to response
- Duration of response

Kaplan Meier survival curves and parameters showing time-to-first observed response outcome will be summarized by parent study treatment, by anti-TNF use and overall. Summary statistics that will be presented will include minimum, maximum, the 25th and 75th percentiles, 95%

confidence intervals on the median (using the method of Brookmeyer and Crowley), and proportion of the events and censored data. Parent study treatment comparison will be performed using log-rank test.

Kaplan-Meier plots with descriptive summary statistics will be presented.

6.3.3.2 Remission from Week 16 through week 52

Number and proportion of subjects experiencing maintenance of remission (CDAI score < 150) from week 16 through week 52 and the number and proportion of subjects experiencing remission at week 16 and week 52 will be provided within each parent study treatment group and overall, as well as subgroup by anti-TNF agent use. 95% exact Clopper-Pearson confidence interval (CI) for the proportion will also be presented. Parent study treatment comparison will be performed using Fisher's exact test.

In addition, similar summaries will be provided for remission at week 52 overall and for subjects who achieved remission at week 16

Proportion of subjects who achieved the following response will be provided overall and by parent study treatment:

Remission at week 16 plus 50% reduction in CRP or calprotectin from baseline

Remission at week 52 plus 50% reduction in CRP or calprotectin from baseline

6.3.4 Selected Other Endpoints/Variables

6.3.4.1 MAP Buffy Coat culture

All summaries will be done by parent study treatment and overall.

Number and percent of subjects will be summarized for MAP buffy coat culture (positive/negative) by scheduled visit (baseline, weeks 16, 26 and 52), 95% exact Clopper-Pearson confidence interval (CI) will be provided for the proportion of positive MAP buffy coat culture.

Shift table from baseline to each post baseline visit (weeks 16, 26 and 52) will be summarized.

6.3.4.2 Endoscopic Assessment Based on CDEIS and SES-CD

The Crohn's Disease Endoscopic Index of Severity (CDEIS) is a validated quantitative measure of disease severity upon endoscopy. The score ranges from 0-44 based upon the extent and severity of inflammation and ulcers seen during endoscopy of the colon. A response is a decrease in score from baseline.

The Simple Endoscopic Score for Crohn's Disease (SES-CD) is a validated quantitative measure of disease severity upon endoscopy that is based on four endoscopic variables (presence and size of ulcers, extent of ulcerated surface, extent of affected surface, and presence of narrowing). Each

variable is assessed in each of the five ileocolic segments: rectum, sigmoid and left colon, transverse colon, right colon, and ileum. Each of the four SES-CD variables is scored from 0 to 3, with the sum of the scores for each variable ranging from 0 to 15 (Total SES-CD score range 0–60).

CDEIS data are presented in data listing only.

The SES-CD total scores by visit (baseline and weeks 16 and 52) and change from baseline scores to week 16 and 52 will be summarized descriptively for subjects who consent to undergo colonoscopy by parent study treatment and overall. The summary statistics include number of observations, mean with 95% CI, standard deviation, median, inter-quartile ranges, minimum, and maximum.

Number and proportion of subjects who achieved success defined below and corresponding 95% exact Clopper-Pearson CI for the proportion will be provided.

- by 25% improved in SES-CD from baseline to week 16 and 52. Success is achieved if the SES-CD score is decreased by 25%.
- by 50% improved in SES-CD from baseline to week 16 and 52. Success is achieved if the SES-CD score is decreased by 50%.

Paired response between each of above defined improvement and corresponding CDAI remission (<150) at each visit will be compared using exact McNemar’s test. Similarly, paired response between each of above defined improvement and corresponding CDAI response (≥100% decrease from baseline) at each visit will be compared using exact McNemar’s test.

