2.1.4 Selected Other Objectives

MAP Detection:

1. To estimate the proportion of subjects with a MAP positive blood PCR assay at baseline (week 0 of the open label phase).
2. To estimate the proportion of subjects with a change in MAP blood PCR assay status after 16 weeks of treatment compared to baseline (week 0 of the open label phase).
3. To estimate the proportion of subjects with a change in MAP blood PCR assay status after 52 weeks of treatment compared to baseline (week 0 of the open label phase).
4. To make sequential comparisons of MAP blood PCR assay results per subject.
5. To estimate the proportion of enrolled subjects with a MAP positive blood culture at baseline (week 0 of the open label phase).
6. To estimate the proportion of subjects with a change in MAP blood culture status after 26 weeks of treatment compared to baseline (week 0 of the open label phase).
7. To estimate the proportion of subjects with a change in MAP blood culture status after 52 weeks of treatment compared to baseline (week 0 of the open label phase).

Because the buffy coat is the actual component of blood that is cultured, MAP blood culture should be considered equivalent to MAP buffy coat culture. Because the development of a MAP

blood PCR assay is still in progress, MAP detection objectives 1-4 will comprise the contents of a later report and will not be addressed in tables, listings, or figures of this clinical study report.

Endoscopic Changes in Those Subjects Who Undergo Colonoscopy:

8. To estimate the change from baseline in the mean Crohn's Disease Endoscopic Index of Severity (CDEIS) after 16 and 52 weeks of treatment).
9. To estimate the change from baseline in the total Simple Endoscopic Activity Score weeks (SES-CD) after 16 and 52 weeks of treatment.
10. To make a comparison of success rates of (Δ CDEIS and SES-CD) defined by 25% and 50% improvements.
11. To estimate the correlation between the change from baseline in the endoscopic index (Δ CDEIS) and the clinical index (Δ CDAI) after 16 and 52 weeks of treatment.
12. To make a comparison of success rates of (Δ CDEIS) defined by 25% and 50% improvements and CDAI defined remission.
13. To make a comparison of success rates of (Δ CDEIS) defined by 25% and 50% improvements and CDAI defined response.
14. To make a comparison of success rates of (Δ SES-CD) defined by 25% and 50% improvements and CDAI defined remission.

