2.2.4.2 Endoscopic Change Endpoint/Variables

- Change from baseline to week 16 and 52 in Crohn's Disease Endoscopic Index of Severity (CDEIS) and Simple Endoscopic Score for Crohn's Disease (SES-CD). The CDEIS and SES-CD are endoscopic scoring systems for the assessment of CD.
- Success rate by 25% improved in CDEIS from baseline to week 16 and 52. Success is achieved if the CDEIS score is decreased by 25%.
- Success rate by 50% improved in CDEIS from baseline to week 16 and 52. Success is achieved if the CDEIS score is decreased by 50%.
- Success rate by 25% improved in SES-CD from baseline to week 16 and 52. Success is achieved if the SES-CD score is decreased by 25%.
- Success rate by 50% improved in SES-CD from baseline to week 16 and 52. Success is achieved if the SES-CD score is decreased by 50%.
- Comparison of success rate of by 25% and 50% improved in CDEIS from baseline to week 16 and 52 vs CDAI defined remission.
- Comparison of success rate of by 25% and 50% improved in CDEIS from baseline to week 16 and 52 vs CDAI defined response.
- Comparison of success rate of by 25% and 50% improved in SES-CD from baseline to week 16 and 52 vs CDAI defined remission.
- Comparison of success rate of by 25% and 50% improved in SES-CD from baseline to week 16 and 52 vs CDAI defined response.

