6.5 Changes to Statistical Analysis Methods Planned in the Protocol

Because the buffy coat is the actual component of blood that is cultured, MAP blood culture should be considered equivalent to MAP buffy coat culture. Because the development of a MAP blood PCR assay is still in progress, MAP detection objectives 1-4 will comprise the contents of a later report and will not be addressed in tables, listings, or figures of this clinical study report.

Change from baseline in the Short Form-36 Health Survey (SF-36) total score have been removed to be consistent with parent study. Summary of domains are removed in SAP.

Correlations between the change from baseline in SES-CD and the change from baseline in CDAI to week 16 and 52 are not included in SAP.

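### SAP 6.3.4.2 reduces CDEIS to a listing and 6.5 does not declare it, so objectives 8 and 11–13 have no planned analysis and objective 10 is covered only for SES-CD

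*SAP*

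**What the plan says.** **Objectives (SAP 2.1.4).** Objective 8 is "To estimate the change from baseline in the mean Crohn's Disease Endoscopic Index of Severity (CDEIS) after 16 and 52 weeks of treatment". Objective 10 is "To make a comparison of success rates of (Δ CDEIS and SES-CD) defined by 25% and 50% improvements". Objective 11 begins "To estimate the correlation between the change from baseline in the endoscopic index" and names CDEIS and CDAI as the two indices. Objective 12 is "To make a comparison of success rates of (Δ CDEIS) defined by 25% and 50% improvements and CDAI defined remission", and objective 13 is its counterpart for CDAI response.

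**Endpoints (SAP 2.2.4.2).** The list contains CDEIS change, "Success rate by 25% improved in CDEIS from baseline to week 16 and 52", the same at 50%, and comparisons of CDEIS success with CDAI remission and with CDAI response. It contains no correlation. The CDEIS–CDAI correlation is an objective in the SAP and an outcome measure in the protocol.

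**Analysis (SAP 6.3.4.2).** After describing both indices as validated, the section says "CDEIS data are presented in data listing only". The descriptive summaries, success proportions and McNemar tests that follow are written for SES-CD.

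**Outputs (SAP 8.1).** Tables 14.2.6.1 to 14.2.6.3 all concern SES-CD. CDEIS appears only as Listing 16.2.6.7.

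**Declared changes (SAP 6.5).** The one endoscopic entry is "Correlations between the change from baseline in SES-CD and the change from baseline in CDAI to week 16 and 52 are not included in SAP".

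**The concern.** The front half of the SAP commits to estimating and comparing CDEIS results, while the back half plans none of this. A programmer who follows 6.3.4.2 and 8.1 will produce a study report in which several stated objectives have no corresponding result, although the visit schedule provides for CDEIS and SES-CD to be scored at the optional colonoscopies.

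The silence in 6.5 makes this worse. That section names the SES-CD correlation as dropped, so a reader would reasonably take the CDEIS correlation to be kept, yet no method for it appears anywhere. With one correlation withdrawn and the other left without a method, nothing in the plan relates the size of endoscopic change to the size of clinical change. McNemar's test does not fill that gap. It compares two paired proportions and says nothing about how closely two continuous changes move together.

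Two endoscopic indices were planned and one is analysed, with no reason given. Even when the choice is innocent, it should be explained where departures from the protocol are recorded.

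**Working it through.** The point is textual, so the check sets the sections side by side. The SAP's only precision figure (6.1.7) is a maximum 95% Clopper-Pearson width of 0.203 for 100 subjects. It reproduces: 50 of 100 gives 0.3983 to 0.6017, a width of 0.2034. It does not bear on this point, because the number of subjects with colonoscopy is not stated.

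**Step 1. Each endoscopic objective against the analysis section.**

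| Objective (2.1.4) | Subject | Planned in 6.3.4.2? |
|---|---|---|
| 8 | CDEIS change | No, listing only |
| 9 | SES-CD change | Yes |
| 10 | 25%/50% success, CDEIS and SES-CD | SES-CD side only |
| 11 | Correlation of CDEIS change with CDAI change | No |
| 12 | CDEIS success and CDAI remission | No |
| 13 | CDEIS success and CDAI response | No |
| 14 | SES-CD success and CDAI remission | Yes, exact McNemar |
| 15 | SES-CD success and CDAI response | Yes, exact McNemar |

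Four of the eight objectives (8, 11, 12, 13) have no planned summary, estimate or test. A fifth (10) is covered on one side. If objective 10 is read as a direct comparison of the two indices' success rates, it is not covered at all.

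**Step 2. Endpoints in 2.2.4.2.** Of the nine bullets, four concern CDEIS alone: 25% success, 50% success, comparison with remission and comparison with response. None of the four has a planned analysis. The CDEIS half of the first bullet (change from baseline) has none either.

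**Step 3. Could the McNemar paragraph cover CDEIS?** It applies to the improvements defined above it in the same section. Those are the 25% and 50% SES-CD criteria, so it does not.

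**Step 4. Outputs.** Section 8.1 agrees with 6.3.4.2: three SES-CD tables, no CDEIS table or figure, and one CDEIS listing.

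**Step 5. Is the reduction declared?** Section 6.5 covers the MAP PCR assay, SF-36 and the SES-CD correlation. SF-36 is a useful comparison: 6.3.4.3 also reduces it to listings, and 6.5 says that its summaries were removed. By the SAP's own practice, the CDEIS reduction belonged there too.

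**Step 6. Does the precedence rule settle it?** Section 6.1.1 puts the SAP above the protocol on methods. Here 2.1.4 and 2.2.4.2 of the SAP conflict with 6.3.4.2 and 8.1 of the same SAP, so the rule does not apply.

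**Step 7. Can the SES-CD text be copied unchanged?** No. In its McNemar paragraph, 6.3.4.2 describes CDAI response as a decrease of at least 100%. Sections 2.1.2 and 2.2.2 define it as a reduction of at least 100 points. Copying the text would carry that error into the CDEIS analysis.

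**The case against.** The strongest reply is that the choice of SES-CD is open and written in advance: 6.3.4.2 states it and 8.1 matches it. Endoscopic change and its relation to CDAI remission and response are still analysed, using an index that the SAP calls validated. Individual CDEIS and CDAI values will be listed (Listings 16.2.6.7 and 16.2.6.1), and section 7 allows further exploratory work. These objectives belong to the last of four endpoint families and depend on an optional colonoscopy, so estimates may be imprecise. On this view the defect is a missing entry in 6.5.

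Much of this stands, and it sets the size of the point. It does not remove it. SES-CD results do not answer objectives that name CDEIS, and a listing is not an estimate. An analysis chosen under section 7 would be decided at the time of final analysis, so it would not be pre-specified.

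A reader might go further and infer that SES-CD was preferred after results were seen, or that the SAP came too late. The documents do not support this. The SAP carries a date of 23 December 2019, but neither document gives a last-visit, database-lock or data-access date, and the protocol asks only for a SAP before study completion.

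**Conclusion.** The inconsistency is real and undeclared. Objectives 8, 11, 12 and 13 have no planned summary, estimate or test, and objective 10 is covered for SES-CD only. The primary and key secondary results are unaffected. It should be corrected, but it does not threaten the trial's main conclusions.

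Two stronger readings should be avoided. A reader might infer that the CDEIS objectives can never be answered; in fact the values are listed, and what is missing is a planned analysis. A reader might also infer that the CDEIS–CDAI correlation is a defined SAP endpoint. It is objective 11 and a protocol outcome measure, but 2.2.4.2 does not include it.

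The conclusion rests on the text of the two documents alone and needs no assumption about the number of colonoscopies or the timing of the SAP.

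**What to change.** **Preferred.** Replace the listing-only sentence in 6.3.4.2 with the following for CDEIS at weeks 16 and 52:
- change from baseline with its 95% confidence interval;
- 25% and 50% success proportions with exact Clopper-Pearson intervals;
- paired comparison of each success criterion with CDAI remission and CDAI response, with response defined as in 2.2.2 (a reduction of at least 100 points);
- a correlation of change in CDEIS with change in CDAI, with a confidence interval. Neither document names a coefficient; Spearman's would be a reasonable choice.

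Add the tables to 8.1, and correct the percentage wording of CDAI response in the existing SES-CD text at the same time.

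**Minimum alternative.** If the sponsor has a reason to keep CDEIS as a listing, state the decision and the reason in 6.5, remove the CDEIS endpoints from 2.2.4.2, and mark objectives 8 and 10 to 13 accordingly. Objective 10 would then be limited to SES-CD.

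**Cost.** The preferred route needs a few extra tables, largely from the SES-CD programs, and one new program for the correlation, since the SES-CD correlation is itself dropped. It needs no new procedure or data collection. Intervals may be wide because colonoscopy is optional. The alternative costs only text, but it leaves the CDEIS objectives without results.

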2.2.1 Primary Endpoint/Variable: Remission

In general use of rescue medication is considered as treatment failure (not achieving remission or response) if there are any new use of rescue medication to treat CD or increased rescue medication dose from baseline prior to any remission or response assessment. Please refer to section 6.1.6 for more details.

The primary variable is the proportion of subjects who experienced remission at Week 16 after the initiation of open-label phase, where remission is defined as a subject having a Crohn's Disease Activity Index (CDAI) score of <150 . Subjects who have a Week 16 CDAI measurement ≥ 150 or who do not have a CDAI measurement at Week 16 will be classified as not having achieved remission at that time point. Initiation of open-label phase is the first dosing time of open-label phase and from here and after it would be reference as initiation.

The CDAI is used to assess the activity of CD; higher scores indicate more active disease.

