6.1.6 Rescue Medications Use

Subjects rescued with the following treatments or whose baseline doses/regimens are increased to treat new or unresolved CD symptoms may remain on the study drug at the discretion of the investigator and continue to be assessed at all scheduled study visits:

- Oral or rectal 5-ASA compounds
- Azathioprine or 6-mercaptopurine (6-MP) or methotrexate
- Total parenteral nutrition as treatment of CD
- Systemic or rectal corticosteroid therapy
- Anti-TNF or other biologic agent

In analyses of remission or response, subjects who initiate new treatment or increase concomitant medication to treat CD symptoms will be considered as treatment failures.

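### The SAP's McNemar tests pair SES-CD success, defined by score alone, with CDAI outcomes that count rescue as failure, so rescue can shift the comparison in one direction only

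*SAP*

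**What the plan says.** **The test.** SAP 6.3.4.2 plans, for the 25% and the 50% SES-CD improvement: "Paired response between each of above defined improvement and corresponding CDAI remission (<150) at each visit will be compared using exact" McNemar's test. It then adds the second CDAI outcome: "Similarly, paired response between each of above defined improvement and corresponding CDAI response". That section prints the response criterion with a percent sign. SAP 2.1.2 gives it as a reduction of at least 100 points, which is the meaning used here.

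**The endoscopic member of the pair.** The definition rests on the score only. At the lower level 6.3.4.2 reads "Success is achieved if the SES-CD score is decreased by 25" per cent; at the higher level 2.2.4.2 reads "Success is achieved if the SES-CD score is decreased by 50" per cent. Neither section mentions rescue.

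**The CDAI member of the pair.** SAP 2.2.1 states "In general use of rescue medication is considered as treatment failure (not achieving remission or response") when new or increased CD medication precedes the assessment. SAP 6.1.6 repeats it: "In analyses of remission or response, subjects who initiate new treatment or increase concomitant medication to treat CD symptoms will be considered as treatment failures".

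**Follow-up after rescue.** Under 6.1.6 rescued subjects "may remain on the study drug at the discretion of the investigator and continue to be assessed at all scheduled study visits", so SES-CD scores after rescue can exist.

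**Who is analysed.** SES-CD scores are "summarized descriptively for subjects who consent to undergo colonoscopy by parent study treatment and overall". The size of that subset is not given.

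**The concern.** McNemar's test uses only the discordant pairs, so anything that creates or removes discordance on one side goes straight into the statistic. Take a subject rescued at week 20 whose week 52 CDAI is below 150 and whose SES-CD has halved. On observed scores both measures improved. With the rescue rule on one member only, the subject is entered as SES-CD success and CDAI failure.

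SAP objectives 14 and 15 (2.1.4) ask for a comparison of SES-CD success rates with CDAI-defined remission and response. If the members of a pair follow different rescue rules, that comparison mixes the difference between the measures with the frequency of rescue. Week 52 is more exposed than week 16 because rescue accumulates over time.

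**Working it through.** **1. The plan's own figure.** The only precision figure is in SAP 6.1.7: a maximum 95% Clopper-Pearson width of 0.203 with 100 patients. For 50 of 100, the limits are the 2.5% quantile of Beta(50, 51) and the 97.5% quantile of Beta(51, 50), that is 0.3983 and 0.6017. The width is 0.2034, so the figure reproduces. No figure is stated for the McNemar tests.

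**2. Direction.** Write each pair as (SES-CD, CDAI), with 1 for success. Under the literal reading, rescue sets CDAI to 0 and leaves SES-CD alone.

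| Pair on observed scores | Pair after the rescue rule | Effect on the test |
|---|---|---|
| (1,1) | (1,0) | adds a discordant pair favouring SES-CD |
| (0,1) | (0,0) | removes a discordant pair favouring CDAI |
| (1,0) | (1,0) | none |
| (0,0) | (0,0) | none |

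Both changes push the same way. The SES-CD rate is untouched. The CDAI rate falls by the proportion of subjects who were rescued and whose observed CDAI met the criterion, and the difference in rates shifts by exactly that proportion. This step needs no assumed rate.

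**3. Number of subjects needed.** Let b be the number of (1,0) pairs and c the number of (0,1) pairs, with c the smaller. The exact two-sided p is 2 × P(X ≤ c), where X is Binomial(b + c, 0.5).

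- 5 v 0: 2 × (1/32) = 0.0625
- 6 v 0: 2 × (1/64) = 0.031
- 10 v 2 (8 added to 2 v 2): 2 × (1 + 12 + 66)/4096 = 0.039
- 12 v 3 (9 added to 3 v 3): 2 × (1 + 15 + 105 + 455)/32768 = 0.035
- 15 v 5 (10 added to 5 v 5): p = 0.041

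The added subjects are those who were rescued and met both criteria on observed scores. The background discordance is assumed.

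**4. Rejection rates under assumed rates.** Inputs, none of them in the documents: both success rates 50% before rescue is scored, 15% discordance each way, rescue independent of both outcomes, two-sided alpha 0.05. With r the rescued proportion, the literal reading gives

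- P(1,0) = 0.15 + r × 0.35
- P(0,1) = 0.15 × (1 − r)

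The difference is 0.5 × r, so r = 0.2 gives 0.22 − 0.12 = 0.10. Simulation with 40,000 runs per cell gives these probabilities of p < 0.05:

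| Subjects with paired data | 10% rescued | 20% rescued | 30% rescued |
|---|---|---|---|
| 20 | 0.022 | 0.049 | 0.099 |
| 30 | 0.039 | 0.087 | 0.177 |
| 50 | 0.056 | 0.164 | 0.345 |
| 100 | 0.101 | 0.335 | 0.662 |

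With rescue counted as failure on both members, the rate stays at or below 0.030 in every cell.

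**The case against.** **The SAP does not say that rescue is ignored for SES-CD.** A reader might infer a deliberate choice, but the documents are only silent. The rule in 6.1.6 covers analyses of remission or response, and the SAP also uses the word response for endoscopic outcomes: 6.3.4.2 calls a fall in CDEIS a response, and the titles of Tables 14.2.6.2 and 14.2.6.3 call SES-CD success an endoscopic response. A programmer could apply the rule to both members. Conversely, 6.3.4.2 gives the CDAI threshold in brackets, so a score-only reading of both is arguable too. This stands as a caveat. Because 2.2.4.2 and 6.3.4.2 name the outcome success and define it by score, the literal reading remains the natural one, and the ambiguity is itself a reason to add a sentence.

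**The objectives ask for a comparison of rates, not agreement.** Correct. McNemar's test compares the two marginal rates, and a relative SES-CD change and an absolute CDAI threshold need not have equal rates in any case. A p-value below 0.05 therefore carries limited weight. The shift in the difference remains.

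**Different rescue handling can be legitimate.** For stand-alone rates, yes: reporting observed endoscopic change regardless of rescue is an acceptable descriptive choice. In a within-subject comparison, the difference in rules enters the statistic.

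**The numbers may be small.** Each affected subject must consent to colonoscopy, be rescued, remain under assessment and meet both criteria. That six such subjects will occur cannot be shown from the documents, and perfect agreement otherwise is unlikely. This stands.

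**Conclusion.** The point holds as a one-directional distortion of the SES-CD versus CDAI comparison under the literal reading of the SAP. The direction is certain on that reading; the size is not. The p-value of 0.031 with six subjects assumes no other discordance, and step 4 rests wholly on assumed rates.

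Two stronger conclusions are tempting. One is that the tests will produce false findings; that would need the rescue rate and the number of colonoscopies, which are not stated. The other is that the SES-CD success rates or the trial's main results are compromised. They are not: primary and key secondary analyses do not use these pairs, the endpoints belong to the last of the four families in SAP 2.2, no alpha is set for these tests, and the list in SAP 8.1 has no separately titled SES-CD versus CDAI table. The matter concerns the interpretation of objectives 14 and 15 and is cheap to settle before analysis.

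**What to change.** Add a sentence to SAP 6.3.4.2, limited to the McNemar tables, stating that rescue is handled identically for both members of each pair. Two options do this:

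- **Observed CDAI.** Use CDAI below 150, or a reduction of at least 100 points, without the rescue rule. The CDAI rates in these tables may then exceed those in the main remission and response tables, which a footnote should explain.
- **One visit-level flag.** Score both SES-CD success and the CDAI outcome as failure if rescue preceded the week 16 or week 52 CDAI assessment. Paired SES-CD success rates may then be slightly lower than the stand-alone rates, and rescued subjects become joint failures whatever their scores.

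The flag should not be keyed to the colonoscopy date. Under the footnotes to SAP 4.1.1, the week 16 colonoscopy falls up to 14 days after the visit and the week 52 colonoscopy 8 to 20 days before it. With a colonoscopy-dated flag, rescue between the week 52 colonoscopy and the visit would still give SES-CD success with CDAI failure. Rescue between the week 16 visit and the colonoscopy would give the reverse. The visit-level flag is already needed for the CDAI endpoints.

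The stand-alone 25% and 50% SES-CD success rates can stay as planned. The cost is one extra derivation.
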